Impact of combining rTMS with motor training (Aim 2b): Motor training strategies used in individuals with cervical SCI often focus on increasing volitional arm muscle activation through strength training, electrical stimulation, and general exercises (see Spooren et al., 2009). While these studies reported that motor training enhances hand motor function, behavioral improvements remain limited. Over the last decades, high frequency rTMS applied over the motor cortex has been shown to induce changes in motor cortical excitability (see section above). Since the mechanisms underlying these effects are related to CNS plasticity, rTMS has been combined with motor training as a tool for enhancing motor function in individuals with movement disorders.

Impairment in motor function is a major deficit in veterans with spinal cord injury (SCI). While rehabilitative interventions have shown success in improving aspects of hand motor function their overall effects remain limited. The goals of this study are to examine the physiology of nervous system pathways contributing to the control of movements after cervical SCI, and to promote the recovery of upper and lower extremity movements by using non-invasive brain stimulation and motor training. We focus on both hand and arm function, which are necessary for most of our daily-life activities, as well as lower extremity movement; therefore, our results may directly impact the quality of life for veterans and their caregivers by enhancing their independence and level of care.

C. Study Design

This study will focus on two basic aspects involved in upper and lower extremity motor function, and how these are affected after chronic SCI using a randomized sham control design with single blind.

Methodology:

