(B). Motoneuronal excitability (reflected by F-wave persistence and amplitude): F-waves will be tested by using supra-maximum stimulus intensity (120% of the maximal motor response) to the ulnar nerve at the wrist and the median nerve at the elbow. The anode and cathode will be approximately 3 cm apart and 1 cm in diameter. We will examine F-waves in first dorsal interosseous, flexor and extensor carpis radialis muscles.

Phase 2

Aim 2a. Enhance recovery of motor function by using non-invasive repetitive transcranial magnetic stimulation (rTMS)

To accomplish this aim we propose to complete two main experiments. First we will use rTMS to test the hypothesis that *rTMS induced cortical plasticity during movement will enhance voluntary output in hand muscles (as measures by electromyography and Jebsen Taylor Test) after spinal cord injury (Aim 2a)*. Second, we will combine precision grip and wrist training with rTMS to test the hypothesis that *precision grip training outcomes will be enhanced by rTMS induced cortical plasticity (aim 2b)*.

Experiment 1 (Aim 2a)

Participants will be randomly assigned to three groups: (1) rTMS, (2) Sham rTMS and (3) sham rTMS over control brain area. Randomization will be performed by lottery (i.e. Drawing from an envelope a piece of paper indicating the intervention). In the first two groups, rTMS stimulation will be targeting finger and wrist muscles during precision grip and write voluntary contractions. In the last group, rTMS will be applied over the dorsolateral prefrontal cortex (DLPFC) or at the leg presentation of the primary motor cortex, or at other related control area as needed. Each subject will be asked to participate in all sessions separated by a washout period of approximately one week. During testing, subjects will be seated in an armchair with both arms flexed at the elbow by 90 degrees. In each group we will use the same apparatus described in Aim1. At the start of the experiment subjects will perform 3 brief MVCs (3-5s) into index finger abduction and wrists flexion and extension, separated by 30 seconds. The maximal forces will be used to set targets for subsequent submaximal contractions.

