Screening Interview: Identifiable information collected during either the screening interview will be destroyed if the potential subject does not qualify. If the subject does qualify and ultimately enrolls into this research, all information collected will become part of their research record. All security precautions that are reflected in this protocol will apply.

Data Collection and Storage: Research records will be retained in accordance with the Veterans Health Administration (VHA) Records Control Schedule. The Federal Privacy Act protects the confidentiality of medical records. Electronically-stored medical information collected from study participants will be kept on a VA server. Electronic data recorded during experimental sessions will be kept on fully-secured computers (password protected) on a VA server. Unique subject identifiers (i.e., a code accessible only to the PI and AI) will be used to label all electronic data files.

F. Sample Size

Up to 500 participants (250 SCI, and 250 control subjects) will be recruited to participate in this study at the VAMHS and at the University of Miami. Based on our previous protocols testing spinal cord injured subjects and healthy control subjects, we have added a 25% attrition rate to the number of subjects we plan to enroll in the study.

All participants will be between 18 and 85 years of age. We plan to recruit both veterans and non-veterans.

G. Data analysis is consistent with the study objective

Aim 1: Repeated-measures ANOVA and Tukey post hoc test will be used to assess the effect of TASK (rest, precision grip/wrist flexion, and precision grip/wrist extension) and GROUP (SCI, controls) on physiological measurements.

Aim 2a: Repeated measures ANOVA and Tukey post hoc test will be used to determine the effect of TIME (0,10, 30, 60 min after a single rTMS session), STIMULATION (rTMS, sham rTMS over control brain area) on physiological and behavioral measurements.

Aim 2b: repeated measures of ANOVA and Tukey post hoc analysis will be used to determine effects of GROUP (training + rTMS, training + sham rTMS), TIME (sessions number 1,5,10 and follow up 1,2, and 3 months) on physiological outcomes and motor performance.

H. Privacy and Confidentiality:

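### Aim 2a is written both as three randomised groups and as every participant attending all sessions; the plan must state one design, how session order is set, and whether STIMULATION is within or between participants.

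*Combined protocol and SAP*

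**What the plan says.** Section C describes the whole study only as "using a randomized sham control design with single blind", without saying parallel or crossover.

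Phase 2, Experiment 1 (Aim 2a) then gives two descriptions in one paragraph:

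- **Parallel wording.** "Participants will be randomly assigned to three groups: (1) rTMS, (2) Sham rTMS and (3) sham rTMS over control brain area". The lottery is explained as "Drawing from an envelope a piece of paper indicating the intervention", so the paper names one intervention and not a sequence. The text goes on to speak of groups, for example "In the first two groups, rTMS stimulation will be targeting finger and wrist muscles".
- **Crossover wording.** "Each subject will be asked to participate in all sessions separated by a washout period of approximately one week".

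Section G analyses Aim 2a by repeated-measures ANOVA with the factors "TIME (0,10, 30, 60 min after a single rTMS session), STIMULATION (rTMS, sham rTMS over control brain area"). It does not declare STIMULATION as within or between participants and has no period or sequence term. For Aim 2b the same section uses a different factor name: "determine effects of GROUP (training + rTMS, training + sham rTMS), TIME (sessions number 1,5,10 and follow up 1,2, and 3 months").

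Experiment 1 also provides for measurements before as well as after stimulation. The TIME levels in section G count from the stimulation session onward and do not name a pre-session value.

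**The concern.** The two descriptions are different trials. In one, each person contributes one condition and the comparison is between people. In the other, each person contributes three conditions and is their own control. The error term for the main Aim 2a test depends on which applies, and section G leaves an analyst to choose, possibly after seeing data.

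If the crossover is meant, the plan also omits how the order of conditions is set. Washout deals with carryover, not with practice. Practice is plausible here: the Aim 2a hypothesis names the Jebsen Taylor test, which is timed, and the force task has three sets of 20 repetitions. With a fixed order, gains from repeating these tasks would be read as a stimulation effect.

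Finally, Experiment 1 lists three conditions while section G prints two levels, so one condition has no stated place in the analysis.

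**Working it through.** **No figure to reproduce.** Section F gives up to 500 participants (250 SCI, 250 controls) for the whole study, with 25% attrition. It gives no number for Aim 2a and no alpha, power, effect size, SD or within-person correlation. Everything below is therefore illustrative. Assumptions: two-sided alpha 0.05, 80% power, one pairwise contrast, standardised difference d = 0.5, no dropout or multiplicity adjustment, and correlation rho between a person's sessions as shown.

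**1. Can the two descriptions be reconciled?** One could read the sessions as repeats within one assigned group. But section G measures TIME after a single stimulation session, and with one such session per person there is nothing to wash out. The harmless reading does not work.

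**2. Crossover data analysed as independent groups.**

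- True variance of a condition contrast: 2σ²(1 − rho)/N.
- Variance the independent-groups analysis would use: 2σ²/N.
- Inflation of the standard error: 1/sqrt(1 − rho).
- Actual type I error: 2[1 − Φ(1.96/sqrt(1 − rho))].

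| rho | SE inflation | Actual type I error |
|---|---|---|
| 0 | 1.00 | 0.05 |
| 0.3 | 1.20 | 0.019 |
| 0.5 | 1.41 | 0.0056 |
| 0.8 | 2.24 | below 0.0001 |

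The error is conservative. Its price is power, Φ[(d/sqrt(2/N) − 1.96)/sqrt(1 − rho)]. At rho 0.5 and N = 32, (2.00 − 1.96)/0.707 = 0.06, so power is 52% instead of 80%.

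**3. How far apart the two designs are.** Three parallel arms of N/3 give contrast variance 6σ²/N. The ratio to the crossover is 3/(1 − rho): 3, 4.3, 6 and 15 at rho 0, 0.3, 0.5 and 0.8. The factor 3 reflects only that each person gives three sessions. In participants, the parallel design needs 2 × (1.96 + 0.84)²/0.5² = 63 per arm, or 189 in total. The crossover needs 189(1 − rho)/3, which is 44 at rho 0.3 and 32 at rho 0.5 (rounded).

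**4. Session order.** Simulation with no true effect, rho 0.5, 4,000 runs, a linear gain per session and no period term. The rate is for a paired test of two conditions in adjacent sessions under the fixed order.

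| Gain per session | Order | False positives, N = 18 | False positives, N = 36 |
|---|---|---|---|
| 0.2 SD | fixed | 12.5% | 20.5% |
| 0.2 SD | random | 5.0% | 5.3% |
| 0.2 SD | balanced | 4.2% | 4.3% |
| 0.3 SD | fixed | 22% | 42% |
| 0.3 SD | random | 5.3% | 4.6% |
| 0.3 SD | balanced | 3.4% | 3.7% |

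Under fixed order the estimate is biased by the per-session gain. Under random or balanced order it is unbiased.

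**5. Error term in a replacement model.** Each session yields four TIME values. With only a participant random effect, these count as independent evidence on STIMULATION. In simulation (N = 30, no true effect, no baseline covariate), type I error was about 17%, 25% and 34% when session-to-session variance was 0.25, 0.5 and 1.0 times the residual variance. Analysing session means gave about 5%. A participant-by-session effect is therefore needed.

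**The case against.** The strongest reply is that the intent is recoverable. Section G uses GROUP in Aims 1 and 2b, where people differ, and STIMULATION in Aim 2a; a washout has no purpose in a parallel trial. This makes a crossover the likelier reading. It remains an inference, because the paragraph also assigns people to groups by drawing one intervention.

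Three stronger readings are tempting and are not supported:

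- **That the plan analyses crossover data as independent groups.** It never says so; it leaves the factor type undeclared. The inflation figures apply only if someone made that choice, and the error would be conservative.
- **That order effects bias the comparison.** The text describes a lottery, not a fixed order. If order is drawn at random for each person, chance imbalance adds noise but no systematic bias. What can be said is that no control of order is stated.
- **That rho is high.** The documents give none. For values adjusted for a same-session baseline, the correlation between sessions may be low, which is why the range starts at 0.

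The pre-stimulation measurements also count in the plan's favour: a same-session baseline would remove much of the gain from one session to the next. Section G does not say that it is used. The two printed levels may be a punctuation slip, but the text as it stands omits a condition.

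**Conclusion.** The contradiction is real, and nothing elsewhere in the document resolves it. Aim 2a cannot be carried out or analysed as written until one design is stated. This is more than missing detail, because two incompatible instructions are given and the choice fixes the error term.

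The consequences are conditional. Misclassifying STIMULATION in a crossover would inflate the standard error by 1.00 to 2.24 times for an assumed rho of 0 to 0.8, with loss of power. Order bias arises only if order is fixed or systematically unbalanced; its size then equals the practice gain between the sessions compared. Neither outcome is shown to have happened. The undeclared factor type, the absent period term and the missing third level hold regardless of any assumption.

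**What to change.** State one design in Experiment 1 and carry it into section G.

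- **If crossover:** replace the group-assignment wording with a randomised, balanced order of the three conditions (3! = 6 sequences). Analyse STIMULATION as a three-level within-participant factor with period, TIME, STIMULATION × TIME and the pre-session value as covariate, and random effects for participant and for participant-by-session. A repeated-measures ANOVA with the equivalent error strata would also serve.
- **If sessions have already been run:** record the order actually used for each person and put period in the model before analysis. This may apply, since the document carries the date 03/01/19 and gives a start of 11/2015 and completion of 12/2019.
- **If parallel:** delete the sentence on all sessions and washout, and analyse STIMULATION between participants with all three levels.

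The cost is protocol and section G wording, plus a sequence list for participants not yet treated; a new list cannot rebalance those already treated. Because no Aim 2a sample size is stated, adequacy cannot be checked for either option. For the same number of participants the parallel option would be much less precise: at least three times the contrast variance, and more if rho is above 0.

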Lower Extremity Physiological Examination Components:

Range of Motion (ROM): active ankle and hip ROM will be measured by a motion capture system (Opti Track, V120: Tri camera, NaturalPoint, Inc) in sitting and standing position. In sitting, subjects will be instructed to complete maximal voluntary dorsiflexion for 10 times separated for period of 10 sec of rest. In standing, subjects will be instructed to complete maximal voluntary hip flexion for 10 times separated for period of 10 sec of rest. Trunk movements will be avoided during testing. The motion capture system will also be utilized to measure foot drop and hip flexion. Markers will be positioned on the external line of the mid trunk, hip, knee, external malleolus, and the lateral side of the 5th metatarsophalangeal joint. The elevation of the toe above ground level will be taken as a measure of foot drop. The amplitude of toe elevation will be calculated from the distance between the marker placed on the 5th metatarsophalangeal joint and the ground (Barthélémy et al., 2010). The largest distance between these two points will be determined and will be referred to as the highest toe elevation. The presence or absence of the second toe elevation prior to heel strike will be measured by subtracting the excursion of the malleolus marker from the elevation of the toe. Hip angle will be constructed by using the trunk, hip and knee markers.

Pinch Grip Strength:

Will be assessed bilaterally using load cells that will record the force generated by the subject. Force will be applied by the thumb and index finger and will be recorded in Newtons (N).

Modified Ashworth Scale and Pendulum Test:

Will be used to measure spasticity level in subjects with SCI during soft tissue stretching.
(Modified Ashworth Scale; Bohannon and Smith, 1987)

Phase 3

Experiment 2 (Aim 2b) :

Individuals with SCI and healthy controls will be randomly assigned to two groups: (1) training + rTMS, and (2) training + sham rTMS. Randomization will be the same as described above. Training will be complete in approximately 15 sessions over approximately 3 weeks. In each session, stimulation or sham stimulation (approximately 25 minutes) will be applied during precision grip and wrist visuo-motor training (approximately 1 hour).

Training + rTMS group- Training will consist of executing three different grip forces with one hand and simultaneously wrist flexion and extension movements while the contralateral hand is at rest.

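### Aim 2b allocates SCI participants and healthy controls by an envelope lottery with no concealment, log, blocking or stratification described, and its ANOVA has no SCI/control factor

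*Combined protocol and SAP*

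**What the plan says.** The allocation mechanism appears once, under Phase 2, Experiment 1 (Aim 2a): "Randomization will be performed by lottery (i.e. Drawing from an envelope a piece of paper indicating the intervention". Phase 3, Experiment 2 (Aim 2b) adopts it by reference: "Randomization will be the same as described above". That experiment has two parallel arms and randomises both populations: "Individuals with SCI and healthy controls will be randomly assigned to two groups: (1) training + rTMS, and (2) training + sham rTMS".

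Section C gives the blinding only as "using a randomized sham control design with single blind" and does not say who is blinded. Section F gives one overall size: "Up to 500 participants (250 SCI, and 250 control subjects) will be recruited to participate in this study". It is not divided by aim, experiment or arm.

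In section G, the Aim 1 ANOVA has a factor separating SCI from controls. The Aim 2b ANOVA has GROUP (the two training arms) and TIME (sessions 1, 5 and 10, then 1, 2 and 3 months), with no term for SCI status.

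The document does not say who prepares or draws the slips, whether they are sealed or returned, how many there are, whether draws are logged, or whether the two populations are drawn separately.

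**The concern.** Two separate problems follow for Aim 2b.

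**Influence on the draw.** Nothing described would prevent a slip from being redrawn, or reveal that it had been. Nor is whoever enrols kept from working out what comes next. In the sham procedure only the coil behind the head fires, so whoever runs the stimulation can presumably tell the arm. The protocol does not separate that role from enrolment, drawing or outcome testing. Allocation that can be foreseen or altered produces selection bias, which a larger sample does not remove.

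**Unequal SCI shares between arms.** The inclusion criteria make the two populations functionally different: controls must manage full wrist flexion-extension on both sides, while SCI participants need only a small movement. If one arm holds more SCI participants, part of the SCI/control difference enters the rTMS-versus-sham contrast. Stratification would prevent this and a model term would adjust for it; neither is described.

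**Working it through.** **The plan's own figure.** The only sizing figure is 250 + 250 = 500, which adds up. No number per experiment is stated, so every n below is an assumption and is shown as a range.

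**1. Chance of an uneven SCI split.** Let n be the SCI participants in Aim 2b and X the number drawn to rTMS. The event is max(X, n − X) ≥ 0.6n.

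- *Independent draws (or slip returned):* X ~ Binomial(n, 0.5).
- *Fixed 1:1 pool, slips not returned, shared with n controls:* X ~ Hypergeometric (2n slips, n of them rTMS, n drawn by SCI participants).

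| SCI n | Independent draws | Shared fixed pool |
|---|---|---|
| 12 | 0.39 | 0.22 |
| 20 | 0.50 | 0.34 |
| 30 | 0.36 | 0.20 |
| 40 | 0.27 | 0.12 |
| 60 | 0.16 | 0.04 |
| 100 | 0.06 | 0.007 |
| 250 | 0.002 | below 0.001 |

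For n = 20 the event is 12:8 or worse. A split of 13:7 or worse has probability 0.26 with independent draws and 0.11 with the shared pool. The figures are not monotone at small n because splits are whole numbers (for n = 12, the first split past 60:40 is 8:4).

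**2. What an uneven split does to the contrast.** Let Δ be the mean SCI-minus-control difference in the quantity analysed, and p₁ and p₀ the SCI shares of the two arms. Without adjustment, the expected arm difference given the split is the treatment effect plus Δ(p₁ − p₀). In a shared pool with 20 SCI and 20 controls the totals are fixed at 20 per arm, so:

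- SCI 12:8 forces controls 8:12. Shift = Δ(12/20 − 8/20) = 0.20Δ.
- SCI 13:7 forces controls 7:13. Shift = Δ(13/20 − 7/20) = 0.30Δ.

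With independent draws, SCI 12:8 and controls 10:10 give Δ(12/22 − 8/18) = 0.10Δ. The document gives no value for Δ, so the shift stays in units of Δ.

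**3. Power cost of unequal numbers.** For a two-arm comparison with 80% power at 50:50 and two-sided α = 0.05 (both assumed), power at split s is Φ[(1.960 + 0.842)·√(4s(1 − s)) − 1.960]. At s = 0.6 this is Φ(2.802 × 0.980 − 1.960) = 78.4%. At s = 0.7 it is Φ(2.802 × 0.917 − 1.960) = 72.8%.

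**4. Foreseeing the next slip.** If a 1:1 pool is drawn without replacement and someone tracks past draws and always guesses the commoner remaining slip, the average proportion of correct guesses is 71% (pool of 4), 65% (10), 62% (20) or 59% (40), against 50% under concealed independent allocation.

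**5. After the change.** With stratified 1:1 permuted blocks (size 4 for illustration), the arms differ by at most 2 within each population: n = 20 gives 10:10, and n = 30 gives at worst 16:14.

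**The case against.** A lottery is genuine randomisation, and the document is silent about safeguards; it does not say there are none. Draws may be logged, slips may be sealed, and separate envelopes for SCI and controls would fit the text as well as one shared envelope. This stands, and it limits the claim to what is not described. A reader might infer that draws go unrecorded, that slips are redrawn, that unblinded staff handle them, or that both populations share one lottery. The document supports none of these as fact.

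A reader might also extend the uneven-arms argument to Aim 2a, where the lottery is described. That does not follow. Aim 2a speaks of assignment to groups ("Participants will be randomly assigned to three groups: (1) rTMS, (2) Sham rTMS and (3) sham rTMS over control brain area") but also says "Each subject will be asked to participate in all sessions separated by a washout period of approximately one week". On the second wording each participant is their own control and the slip may set only session order.

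The imbalance also depends on size. Section F allows up to 250 SCI participants, and if Aim 2b were that large a 60:40 split would be very unlikely. Unequal numbers alone cost little power. Chance imbalance adds variance and does not systematically favour an arm. Pre/post measurement with TIME in the model also reduces the effect of differences in baseline level. All of this stands. It does not answer the concealment point, and TIME alone does not remove a difference between SCI participants and controls in how much they change.

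**Conclusion.** The point holds for Aim 2b as a gap in described safeguards together with a missing model term. Nothing described protects the draw from influence, and neither design nor analysis deals with unequal SCI shares between arms. It does not show that allocation was or will be compromised, and no stated figure is wrong.

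The size of the imbalance risk rests on unstated numbers and on how slips are handled. It is material at a few dozen SCI participants and negligible at 250. The concealment weakness does not shrink with size, but it cannot be quantified from the document. A change should be made: the method is stated, and a better one is cheap.

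**What to change.** 1. For participants still to be randomised, replace the lottery with a computer-generated list in permuted blocks of varying size, stratified by SCI versus control. Varying the block size keeps the last places in a block from becoming predictable. An existing team member who does not enrol should prepare it.
2. Hold allocations in sequentially numbered, sealed, opaque envelopes, opened only after baseline tests, and log each opening. The protocol gives a start date of 11/2015, so for participants already randomised, report how slips were handled and what records exist.
3. Add SCI/control status to the Aim 2b model, with its interactions with GROUP and TIME. The TIME interaction lets the two populations change differently.
4. For Aim 2a, first reconcile assignment to three groups with attendance at all sessions. If it is a crossover, use a balanced list of session sequences.
5. State the planned numbers for Aim 2b by population and arm, and say who is blinded.

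Cost: one list, a set of envelopes and a log, with no added staff; minor logistics; and a few model degrees of freedom. With the six TIME levels listed, these are 1 for SCI status, 1 for its interaction with GROUP and 5 for its interaction with TIME, plus 5 more if the three-way term is fitted.

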This study will consist of electromyography (surface and intramuscular), peripheral nerve stimulation, and transcranial magnetic stimulation, electrical stimulation, of the hand, arm, leg, and foot representation of the primary motor cortex, as well as MRI scans of the brain. We will examine the physiological measurements of upper and lower extremity muscles (such as in the first dorsal interosseous (FDI), biceps brachii (BIC), anterior deltoid (AD), tibialis anterior (TA), hamstring (HAMS) and quadriceps (QUAD)). This study may occur at the Miami Project to cure Paralysis at the University of Miami. We will include subjects between the ages of 18 and 85, both healthy controls and individuals with chronic spinal cord injuries that occurred at least 6 months prior to recruitment. Both healthy controls and those with spinal cord injuries will be able to perform small hand and arm movements and small leg and foot movements. The primary outcome measures of this study are muscle responses to stimulation with magnetic pulses using TMS and electrical stimulation of a peripheral nerve in the arm or leg. We propose to enhance the recovery of motor function by using new protocols of high frequency non-invasive repetitive TMS (rTMS) and motor training. Repetitive TMS will be used during hand, arm, leg and foot movements in a task-dependent manner to induce cortical plasticity and enhance voluntary output of the muscles associated with those movements. Second, rTMS will be applied in a task-dependent manner during a visuo-motor training task that also involves movements of the hands, arms, legs or feet.

Phase 1

Aim 1. Neural Control of Movements in SCI and Control Subjects

We will use TMS, CMEPS, and peripheral nerve stimulation to test the hypotheses that 'precision grip and wrist movements will be associated with reduced motor cortical (as measured by intracortical inhibition) and spinal inputs (as measured by F-wave persistence and amplitude) to hand and wrist motoneurons after cervical SCI compared to controls'. Subjects will be instructed to perform a precision grip (between index and thumb) and simultaneously wrist flexion or extension movements. Measurements of cortical and motoneuronal excitability will be acquired during movement.

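### The third Aim 2a condition is not defined as sham or active and has no fixed site, yet it is the only comparator in the Aim 2a analysis, which leaves out same-site sham

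*Combined protocol and SAP*

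**What the plan says.** Section C, Phase 2, Experiment 1 (Aim 2a) sets out the conditions: "Participants will be randomly assigned to three groups: (1) rTMS, (2) Sham rTMS and (3) sham rTMS over control brain area". The next sentences describe them. For the hand-area conditions: "In the first two groups, rTMS stimulation will be targeting finger and wrist muscles". For the third: "In the last group, rTMS will be applied over the dorsolateral prefrontal cortex (DLPFC) or at the leg presentation of the primary motor cortex", and then "or at other related control area as needed". There is no rule for who picks the site, when, or on what basis. The same paragraph asks every subject to attend all sessions, with a washout of about one week between them.

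Section G, Aim 2a gives the analysis factor as "STIMULATION (rTMS, sham rTMS over control brain area) on physiological and behavioral measurements". Two levels appear; same-site sham does not.

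The only account of how sham is delivered is in Phase 3, Experiment 2 (Aim 2b), under the training plus sham group. There the coil on the head is not triggered; only a second coil behind the head discharges, into the air.

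On the lower limb, the Methodology text of Section C states: "Repetitive TMS will be used during hand, arm, leg and foot movements in a task-dependent manner to induce cortical plasticity". The Aim 2a hypothesis itself concerns hand muscles (EMG and the Jebsen Taylor test).

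**The concern.** A sham comparator and an active comparator at another site answer different questions. rTMS against sham asks whether stimulation has an effect. rTMS against active stimulation elsewhere asks whether the hand area matters in particular. A null result in the first case is a lack of evidence that stimulation works; in the second it is also what one would see if both sites acted equally.

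Here the label points to one question and the description to the other, and the condition that would settle the matter, same-site sham, is absent from the analysis factor. An Aim 2a result reported from Section G as written would have no agreed interpretation. An open choice of site adds a further unknown, because the comparator may not be the same thing throughout the experiment.

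**Working it through.** No sample size, effect size, SD, alpha or power is given for Aim 2a, so there is no planning figure to reproduce. The check is mainly a comparison of texts.

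**1. Label against description.** The group list in Experiment 1 says sham. The description says rTMS is applied and omits the word sham.

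**2. Does the bare term rTMS settle it?** No. The preceding sentence uses rTMS stimulation for the first two conditions together, and the second of these is sham. The author's usage therefore covers sham as well.

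**3. Does the sham procedure settle it?** No. If the Aim 2b procedure applied, no pulse would be delivered through the coil on the head, so the choice of site would not change the stimulation and condition 3 would nearly duplicate condition 2. That favours the active reading but does not prove it. Nothing says that the Aim 2b procedure applies to Aim 2a.

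**4. Does the rTMS protocol paragraph settle it?** No. It gives one protocol with the coil positioned as in Aim 1, which is the finger and wrist position. That cannot describe a condition placed over a control area.

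**5. Conditions randomised against conditions analysed.**

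| Condition | Experiment 1 | Section G, Aim 2a |
|---|---|---|
| rTMS, hand area | yes | yes |
| Sham, hand area | yes | not listed |
| Control-area condition | yes, sham or active not settled | yes, the only comparator |

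**6. What the listed contrast estimates.** Write A for the mean response to hand-area rTMS, S for sham and C for active stimulation at the control site.

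- Condition 3 is sham: contrast = A − S, the effect of stimulation.
- Condition 3 is active: contrast = A − C = (A − S) − (C − S) = (1 − f)(A − S), with f = (C − S)/(A − S).

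Without S in the model, f cannot be estimated, so the second case cannot be converted back to the first. With all three levels, A − S is estimated directly.

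**7. Lower limb.** The Methodology text plans rTMS during leg and foot movements, and leg range-of-motion measures are described under Phase 2. Section G does not restrict which physiological and behavioural measures are analysed. If condition 3 is active and placed over the leg motor area, it stimulates an area the trial also plans to target. This matters only where lower-limb measures are analysed. The Aim 2a hypothesis and its listed before-and-after measures concern the hand.

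**8. Illustration, only if condition 3 is active.** f is assumed; the documents support no value. Using a normal approximation with two-sided alpha 0.05 (also assumed): power = Φ[(z_α + z_β)(1 − f) − z_α], and the sample size that restores power is multiplied by 1/(1 − f)². For 80% power, z_α + z_β = 1.960 + 0.842 = 2.802. At f = 0.25: 2.802 × 0.75 − 1.960 = 0.141, and Φ(0.141) = 0.556.

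| f | Power from 80% | Power from 90% | N multiplier |
|---|---|---|---|
| 0 | 80% | 90% | 1.00 |
| 0.10 | 71% | 83% | 1.23 |
| 0.25 | 56% | 68% | 1.78 |
| 0.50 | 29% | 37% | 4.00 |

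**The case against.** The strongest reply is that this is loose drafting. Both Experiment 1 and Section G label the condition as sham, and the term rTMS is used for a sham condition one sentence earlier. If the coil-behind-the-head procedure is intended, the comparator is inert and the Section G contrast does test stimulation. Section G may simply have dropped a level from a terse parenthesis, since same-site sham is randomised and every subject is to attend all sessions, so those data would exist. For hand outcomes, the leg motor area is a coherent off-target site. The training experiment (Aim 2b) has a described sham and is not affected.

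Much of this stands, and it rules out several stronger readings:

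- A reader might infer that condition 3 is active and so not inert. The documents do not say so.
- A reader might multiply three sites by two types and count six comparators. Under the only sham described, site makes no difference to the stimulation delivered, so that count does not hold.
- A reader might infer that some participants get sham and others active stimulation within condition 3. Nothing suggests this; the conflict is one of wording.
- A reader might infer that the control could outperform rTMS on leg outcomes. That needs active stimulation, the leg site and a lower-limb analysis together, and the Aim 2a hypothesis names hand outcomes only.

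What the reply does not answer is that an analyst following Section G literally would fit a two-level factor whose comparator is undefined, and would leave out the condition whose meaning is clear.

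**Conclusion.** The point holds in this form: the documents do not establish whether condition 3 of Aim 2a is sham or active, its site is not fixed, and Section G makes it the sole comparator while omitting same-site sham. The Aim 2a contrast as written therefore has no fixed meaning. This rests on the text alone and needs no numerical assumption.

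The size cannot be derived from the documents. If condition 3 is sham, f is 0 and the contrast is not diluted; the defect is then one of definition and of an omitted level. If it is active, the contrast is (1 − f) of the effect against sham, and the power figures illustrate that for assumed f between 0 and 0.50. The leg-area point is conditional on active stimulation and on lower-limb measures being analysed; it does not touch the hand outcomes that Aim 2a names. The point should be settled before Aim 2a is analysed, because it decides what the result means.

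**What to change.** Reconcile Experiment 1 (Aim 2a), the sham description in Experiment 2 (Aim 2b) and Section G:

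- State whether condition 3 is sham or active, the same for every participant, and describe how sham is delivered in Aim 2a.
- Delete the clause that allows another control area as needed and fix one control site in advance. It should not be the leg motor area for any analysis of lower-limb measures.
- In Section G, list three levels of STIMULATION: rTMS, same-site sham and the control-area condition. Name rTMS versus same-site sham as the primary contrast for the effect of stimulation.
- If condition 3 is active, state that rTMS versus condition 3 addresses site specificity only.

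The cost is protocol and analysis wording. Same-site sham is already a randomised condition, so restoring it to the analysis needs no new sessions. The downside is less freedom in choosing the control site.
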